Official Title of the Study: Novel Cognitive Treatment Targets for Epidiolex in Sturge-Weber syndrome: A phase II

trial

NCT Number: NCT 04447846

Date of Document: 29 June, 2021

Principal Investigator: [name]

Date: June 29, 2021

Principal Investigator: [name] Application Number: IRB00204427

JHM IRB - eForm A - Protocol

1. Abstract

a. Provide no more than a one page research abstract briefly stating the problem, the research hypothesis, and the importance of the research.

Importance: With this phase II drug trial, we hope to better understand the utility of cannabidiol (CBD/Epidiolex) for improving the treatment of cognitive impairments in Sturge-Weber syndrome.

Problem: Sturge-Weber syndrome (SWS) is a vascular malformation disorder occurring in about 1 in 20,000 live births, and one of the most common neurovascular disorders. Those affected have vascular malformations in the brain, skin and eye. SWS is associated with lifelong epilepsy and cognitive issues; children develop a range of cognitive impairments, including intellectual disability, ADHD, learning disabilities and autism. Patients often develop anxiety, depression and behavioral issues, as well as migraines and motor impairments.

[name] led and published on an Investigator Initiated trial of Epidiolex for medically refractory seizures in 5 patients with Sturge-Weber syndrome (Kaplan et al, Pediatric Neurology, 2017). Three of the 5 subjects had sustained improvement in their seizures; one became seizure-free. Interestingly, cognitive, mood and behavioral improvements were also noted by these patients and their families. It is possible that these improvements resulted from improved seizure control. However, these improvements were first seen between 1-3 weeks after starting Epidiolex, and occurred sooner than would be expected as a result of improved seizure control. In addition, these anecdotal improvements have been sustained. The following clinical improvements were reported qualitatively in these subjects: 1) improved cognitive function, 2) improved social function, 3) improved mood and behavior, 4) improved motor function and 5) reduced migraine frequency and severity. Therefore, we are interested in doing a follow up study to quantify the improvements noted in the initial study.

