Please note that Epidiolex is FDA approved for the treatment of seizures in Lennox-Gestaut syndrome and Dravet syndrome and is clinically used for the treatment of seizures in Sturge-Weber syndrome and many other medically refractory seizure disorders[1-3]. Epidiolex is **no longer** scheduled and can be prescribed clinically for patients seen remotely. We are studying Epidiolex here in Sturge-Weber syndrome for different indications.

Hypothesis: Cannabidiol (Epidiolex) improves SWS brain function resulting in improved cognitive function, social interactions, mood, motor function and behavior, as well as reduced migraines.

2. Objectives (include all primary and secondary objectives)

We propose a follow up to the initial SWS Epidiolex study which suggested improvements in SWS cognitive, social, and behavioral function and in other neurologic issues. **Primary outcome measure:** Quantify cognition 6 months after initiation of Epidiolex compared to baseline. **Secondary outcome**

measures: The following at 6 months compared to baseline: Social function and mood, frequency and severity of seizures, migraine frequency and severity, and motor outcomes.

3. Background (briefly describe pre-clinical and clinical data, current experience with procedures, drug or device, and any other relevant information to justify the research)

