Cannabidiol for SWS. SWS can be viewed as a model for testing the impact of Epidiolex upon $G\alpha q$, an important regulator of pathways downstream of crucial GPCRs. Furthermore, if Epidiolex improves SWS treatment targets such as anxiety, migraine or cognitive impairments, then this drug may prove more generally useful for these symptoms.

4. Study Procedures

a. Study design, including the sequence and timing of study procedures (distinguish research procedures from those that are part of routine care).

Study Overview: The proposed study will be a phase II trial in 10 participants with Sturge-Weber syndrome brain involvement and cognitive impairments at the Hunter Nelson Sturge-Weber Center at the Kennedy Krieger Institute, led by [name]. We may need to consent additional subjects (N=11) to meet our goal of 10 accrued subjects on study drug. In response to the COVID-19 Pandemic Crisis, all visits and assessments will now be conducted remotely by utilizing a video conference application. If medically required, such as for an adverse event that requires an in-person exam, the subject will be seen on-site in our out-patient neurology clinic. We do not anticipate needing to see subjects on-site, but include this in case it is medically necessary.

After screening, written consent will be obtained remotely (see process below), with baseline measures completed before starting on the study drug. All scheduled visits and assessments will be done remotely.

Done remotely as part of routine care (but in this setting NOT billed as clinical care): History, neurological exam, home weight (families to be sent digit scales to be used), home blood pressure and heart rate (families to be sent digital blood pressure and heart rate equipment) labs (outside lab, see process below), SWS neuroscore, Neuropsych testing and psychiatric exam. The following will also be done remotely and only done for research: Port-wine score, picture taken, NeuroQoL (Neurologic Quality of Life Scale), quantitative measurements of motor, behavior, and social function, and migraine scale.

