Behavior Rating Inventory of Executive Function, Second Edition (BRIEF-2; Gioia, G., Isquith, P., Guy, S., & Kenworthy, L. (2015), Behavior *Rating Inventory of Executive Function, Second Edition*. Lutz, FL: WPS.) is a caregiver report questionnaire designed to assess the behavioral manifestations of executive functions in children ages 5-18 years. Raters assess the child's behavior on a 3-point Likert scale and scores are obtained on the scales such as: Initiate, Working Memory, Plan/Organize, Organization of Materials, Self-Monitor, Task-Monitor, Inhibit, Shift, and Emotional Control. Administration time: 10 mins.

The Social Responsiveness Scale, Second Edition (SRS-2; Constantino, J. N., & Gruber, C. P. (2012). Social Responsiveness Scale—Second Edition (SRS-2). Torrance, CA: Western Psychological Services) enquires about a child's ability to engage in emotionally appropriate reciprocal social interactions in naturalistic settings and includes items that ascertain social awareness, social information processing, capacity for reciprocal social responses, social anxiety/avoidance, and characteristic autistic preoccupations/traits. The SRS-2 generates a singular score that can be used as a measure of severity of social function and which can be used to screen for ASD. Approximate time: 15 – 20 minutes.

Change in Migraine Severity: Change in migraine severity is a secondary outcome measure for this trial. At pre-treatment baseline and after 6 months on the study drug, the subject will complete the "Migraine Specific Quality of Life Questionnaire," reflecting on how migraines affect their daily living. The MSQ has 14 questions and been shown to be a psychometrically valid tool that can be used to reliably measure the impact of migraine among chronic migraine patients. [29] Administration time: 10 minutes

Psychiatric Evaluations: Subjects will undergo baseline behavioral assessments including a semi-structured diagnostic interview in order to obtain DSM-V diagnoses. The diagnostic interview instrument will be tailored for the age and cognitive level of the participant. For pediatric participants, the Kiddie Schedule for Affective Disorders and Schizophrenia (KSADS) will be used. The KSADS is a semi-structured diagnostic interview well established in clinical psychiatric research as the standard method for objectively identifying DSM diagnoses, suitable for clinical research purposes.

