Baseline behavioral profiles will also be obtained by using age-appropriate, well-established standardized instruments commonly used in neuropsychiatry clinical practice. These instruments may include the Behavioral Assessment System for Children (BASC), The Screen for Child Anxiety Related Disorders (SCARED) or Children's Depression Rating Scale (CDRS). A quality of life scale is also expected to be obtained such as the Quality of Life in Epilepsy Scale for adolescents (QOLIE-ad-48).

The use of these instruments will reveal a sophisticated behavioral and psychiatric profile that is the state of the art in clinical behavioral science research. Baseline behavior function and psychiatric diagnoses will be well established prior to treatment and compared to ratings from behavioral profile scales obtained at a follow up stage (Approximate time-3 hours at baseline, 1 hour at follow-up).

Safety of Epidiolex: as measured by the number of adverse events and serious adverse events resulting from study drug.

Change in Seizure Severity: All seizure types will be classified before study entry (most common seizure type are partial motor and partial with impaired consciousness). Seizure frequency for each seizure type will be recorded retrospectively for the month prior to enrollment and at each visit during the study using diaries. In addition, at each visit the parents/caregivers will report the following secondary outcome measures: seizure duration by seizure type, number of episodes of status epilepticus (defined as convulsive seizure lasting longer than 10 minutes), number of uses of rescue medication, and the number of ER visits/hospitalizations.

Change in motor function, as defined by Modified House Classification and selected scales from EDPA and parent-report measures: PEDI-CAT and ABILHAND/ABILHAND-KIDS (as previously described).[30] Video recordings of the Modified House Classification and selected scales from EDPA will be taken for each subject at baseline and at six months follow-up. The video recordings will be reviewed and scored blind by a study team occupational therapist. Administration time: 20 minutes

Laboratory tests and clinical procedures

- 1) Weight and vitals will be monitored at baseline and at each remote visit. (Routine care).

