- 2) **Neuroscores** (as previously described)[31-33] will be assigned at each visit by [name] as per her clinical routine. The SWS neuroscore is comprised the frequency of seizures, extent of hemiparesis, assessment of visual field cut, and degree of cognitive functioning with a total score of 15 possible points. Neurologic exam and general physical exam will also be performed remotely at each visit. (Routine care)
- 3) Participants will be asked at each remote visit about any change in neurologic symptoms. (Routine care)
- 4) For subjects with a facial port-wine birthmark, frontal and profile photograph will be taken under standardized conditions with scoring of the port-wine birthmark (**Port-wine birthmark score**) for percent of face covered, thickness of birthmark, and darkness of birthmark color. Families will be mailed a color chart (see appendix) to hold up next to the subject while photos are being taken. Subjects without any facial port-wine birthmark will only need photographs taken at a single visit to confirm the lack of birthmark. (Research, See Study Visit Table).

Table of Remote Visits	Screening	Baseline	Core	e Phase	Endpoint 6 months		
Visit Number	1	2	3	4	5		
Study Week	-2 ± 14	days 0	4	12 ± 7 days	24 >		
Consent	х						
Physical Exam	Х	Х	Х	Х	Х		
Neuroscore	Х	х	Х	Х	X		
Neuro QoL	Х	Х	Х	Х	Х		
Incl/Excl Criteria	Х	Х	Х	Х	Х		
Past Medical	х						
History Diagnosis of SWS	Х						
Seizure Hx	X	Х	X	X	X		
Previous AED Hx	X				^		
Current Med Hx	Х	х	Х	Х	Х		
Picture Taken		Х			Х		
Rescue Meds	Х	Х	Х	X	Х		
AEDs	Х	Х	Х	Х	Х		
Motor, NP, psychiatric Assessments	<				X ± 7 days		
Labwork							
AED Levels CMP (renal, hepatic)	X		X	X	X X		
CBC	Х		Х	X	Х		
CBD/THC Ratio			Х	X	X		
Urinalysis	Х		Х	X	X		
Pregnancy Test (if applicable)	Х		Х	Х	Х		
Safety							
Adverse Events check		X	X	X	Х		
Safety Calls:		←		Bi-monthly			
Continue or Remove?	х	х	Х	Х	Х		
Patient Reported Outcomes			Х	х	Х		

- 5) CBC, LFT, BUN, creatinine levels, electrolytes, and urinalysis will be measured at each visit (screening, 1, 3, and 6 months on drug). Concomitant AED plasma concentrations will be measured at the same visits. CBD/THC ratio in urine will be measured three times; at the one month visit, at the three month visit, and at the 6 month visit. All lab tests will be done remotely at a site local to the participant and charged to the study budget.

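### Migraine frequency is a stated secondary outcome, but no migraine count is specified at baseline or 6 months; the only named migraine measure is an impact questionnaire

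*Combined protocol and SAP*

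**What the plan says.** **The outcome.** Section 2 lists the secondary outcomes, each at 6 months compared with baseline, as "Social function and mood, frequency and severity of seizures, migraine frequency and severity, and motor outcomes". The hypothesis in Section 1 ends with "as well as reduced migraines". Section 1 also includes migraine among the qualitative reports from the previous trial that this one is to put numbers on: "reduced migraine frequency and severity. Therefore, we are interested in doing a follow up study to quantify the improvements".

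**The measurement.** Section 4a (Study Overview) lists among the research-only assessments "quantitative measurements of motor, behavior, and social function, and migraine scale". Section 4a (Change in Migraine Severity) states: "Change in migraine severity is a secondary outcome measure for this trial". The instrument is a 14-question migraine quality-of-life questionnaire, given before treatment and at 6 months, and described as a "psychometrically valid tool that can be used to reliably measure the impact of migraine among chronic migraine patients". Section 7b lists migraine severity, and Section 8a (Other Assessments) also refers to severity.

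**The comparison with seizures.** For the neighbouring outcome in the same Section 2 sentence, Section 4a (Change in Seizure Severity) does specify a count: "Seizure frequency for each seizure type will be recorded retrospectively for the month prior to enrollment", followed by diaries at each visit.

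**The concern.** Section 2 commits the trial to comparing migraine frequency at two time points, and the sections that say what will be collected provide nothing that yields a frequency. An impact score cannot be turned into a number of migraine days: it can improve while the count is unchanged, or the reverse.

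Two things are at stake. First, a stated secondary outcome may have no usable data at the end. Second, with a hypothesis worded as fewer migraines and only an impact score in hand, the write-up needs clear labelling so that the one is not taken for the other. Section 7c says the results are meant to help design a larger trial or guide care, so the distinction has some practical weight.

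**Working it through.** The plan gives no figure to reproduce, and no power or precision calculation applies. The check is a reading of every place where a migraine count could be specified.

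**Sections that say what is measured for migraine**

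| Place | What it specifies | Count of migraines? |
|---|---|---|
| 4a, Study Overview | a migraine scale | no |
| 4a, Change in Migraine Severity | 14-question impact questionnaire, baseline and 6 months | no |
| 7b, Secondary outcome variables | severity | no |
| 8a, Other Assessments | severity | no |

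**Indirect routes**

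- General symptom question (4a, Laboratory tests and clinical procedures, item 3): "Participants will be asked at each remote visit about any change in neurologic symptoms". It asks about change and sets no count or recall period.
- Neuroscore (same list, item 2): covers seizures, hemiparesis, visual field and cognition. It has no migraine component.
- Participant-kept records: a seizure diary and a dosing record (8a, Time Commitment), and a diary for side effects and concerns (8b, Data Safety and Monitoring Plan). A migraine might be noted as a concern, but no count and no pre-treatment period is specified.
- Patient Reported Outcomes row (Table of Remote Visits): content undefined. As extracted, it is marked at Visits 3, 4 and 5 only, so it covers neither of the two pre-dose visits.
- History-taking: past medical history at screening, and history at baseline, at Visits 3 and 4 and at the final evaluation (Table of Remote Visits; 4a, Estimated Time Commitments; 4b, Study Visit 2). No migraine count is specified, but this is the route most likely to hold some information.

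The table's lack of a migraine row carries little weight, because the questionnaire itself has no row of its own either.

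**How many subjects contribute.** No entry criterion in Section 5 requires migraine, so anywhere from 0 to 10 of the 10 subjects could have it.

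**Who could still be given a baseline question.** This version is dated 29 June 2021. The Milestone Table places the last consents (subjects 10 and 11) in February 2021, with no day given. Section 4b allows at most two weeks between Visits 1 and 2, and Section 4a allows one week for the drug to arrive.

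- Longest: 1 February to 29 June = 148 days; 148 / 7 = 21.1 weeks, counted from consent.
- Shortest: 28 February to 29 June = 121 days; 121 − 14 − 7 = 100 days; 100 / 7 = 14.3 weeks, counted from arrival of the drug.

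On the plan's own schedule, the last-consented subject would be about 14 to 21 weeks in: past Visit 4 (week 12 ± 7 days) and before Visit 5 (week 24). No subject would then be undosed. Actual accrual is not stated. Section 4f (replacement of withdrawals in the first two months) and Section 5 (re-enrolment) leave room for new baselines.

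**The case against.** The best reply is that this is a mismatch of one word. Frequency appears as a migraine outcome once, in the short Objectives summary. The fuller sections speak of severity, and Section 7 sets out no analysis of migraine frequency. The trial is a small open-label pilot that does not select for migraine. That stands, and it is why the priority is low. It does not remove the point: Section 2 is where the outcomes are declared, and the seizure outcome in the same sentence received an explicit count.

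Three stronger readings are tempting, and the documents do not support them.

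- A reader might infer that the baseline count is lost for good. History is taken before treatment and at follow-up, some subjects are the center's own patients, and the case report forms are not in the documents. Absence from the protocol does not establish absence from the records.
- A reader might infer that the questionnaire will be presented as showing fewer migraines. Nothing says so; Sections 4a, 7b and 8a consistently label that measure as severity. Misreporting is a risk to guard against, not a plan.
- A reader might conclude that frequency should simply be struck from Section 2. If subjects are already dosed in an unblinded trial, deleting a declared outcome is worse than reporting that it was not measured.

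**Conclusion.** The point holds, at minor priority. Migraine frequency at 6 months against baseline is a declared secondary outcome with no specified data source at either time point. The one named migraine instrument measures impact by the protocol's own description. Some information on frequency may exist in clinical history, but the plan neither asks for a count nor fixes a recall period.

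The effect is confined to part of one secondary outcome among 10 subjects with no control group. The primary outcome is untouched. The conclusion rests on the protocol text alone: the case report forms might contain a migraine item, and actual accrual at the version date is unknown. Correcting the gap makes the outcome reportable, or its absence transparent; it would not make any change attributable to the drug.

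**What to change.** 1. **Any subject not yet dosed, including replacements and re-enrolled subjects:** record migraine days over the preceding month at screening or baseline, and ask the same question at 6 months. This follows the one-month retrospective method already used for baseline seizures.
2. **All subjects:** report the questionnaire as migraine impact, not frequency, and give the number of subjects with migraine at baseline.
3. **Subjects already dosed:** check source records for a documented pre-treatment count. Label any count found as retrospective. Otherwise report migraine frequency as a planned secondary outcome that was not measured.
4. **Text:** reconcile Section 2 with Section 4a (Change in Migraine Severity), Section 7b and Section 8a by a dated amendment that leaves the stated outcome visible and explains what was and was not collected.

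The cost is one recall question at two existing visits, a small recall burden for families, a records check, and an amendment with IRB review. Step 1 may reach no one if the milestone plan held; steps 2 to 4 still apply, since the Milestone Table puts data analysis in September 2021 and the manuscript in November 2021.

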The study drug will be initiated at the baseline visit with [name] reviewing instructions for its use. If a subject lives outside of Maryland, a script will be written and sent to Pharmacord, a pharmacy hub working with Greenwich who will ship the Epidiolex directly to the subject's home within 1 week. If a subject resides in the state of Maryland, a script will be written and sent to the Johns Hopkins Investigational Drug Research Pharmacy, who will ship the Epidiolex directly to the subject's home within 1 week. Receipt of the epidiolex will be confirmed with the subject by the research coordinator and instructions for its use reviewed and any questions answered by [name] if needed.

Follow-up remote visits consisting of lab work (done by script to outside labs), seizure/adverse event reports, an exam (including home reporting of weight, blood pressure and heart rate), neuroscore, , NeuroQoL, and medication review will be held after 1 and 3 months on Epidiolex. After 6 months on Epidiolex, the subjects will undergo follow up remote repeat testing for all the above initial measurements.

If the subject had significant improvements, they will have the option to continue the drug as a part of the extension phase. During the extension phase, the PI will have the ability to change (increase and decrease) dose of Epidiolex and other anti-seizure medications as clinically indicated. The extension phase will involve at least 4 visits (one every 3 months) but subjects may continue on the extension phase until

insurance company coverage is obtained. Study drug will be provided by Greenwich Biosciences until insurance coverage is obtained or other arrangements made to cover the cost of the study drug. At the end of one year, if insurance coverage has not been obtained then Greenwich Biosciences will work with the family through the Greenwich Drug Coverage Program to ensure that subjects benefitting from the drug can continue to receive it. Subjects who did not improve, or do not wish to continue taking Epidiolex, will wean off the drug at this time. If at any point the subject leaves the study, they will be asked to have a follow up remote visit one month after weaning has commenced.

Serious adverse events include those events that: result in death; are life-threatening; require hospitalization or prolongation of existing hospitalization; or create persistent or significant disability, or birth defects.

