Early stopping rules: If a participant experiences a significant health decline or a loss of seizure control (defined as a need to add a new seizure medication), ending assessments will be done, and the subject removed. If the subject experiences a temporary increase in seizures, [name] may take the temporary nature of the increase into account. If the subject has had other benefits to mood, behavior, or neurologic exam that outweigh the risk of an increase in seizures, then [name] may decide to decrease the dose of the study drug since it has been observed that some subjects do well at doses lower than 20 mg/kg/day. Other removal criteria include: death, lost to follow-up, withdrawal of consent for any further data submission, or any other reason the patient, parent, PI or caring physicians think that the subject should be removed. Early withdrawals within the first two months will be replaced.

Study cessation rules. The study will be stopped if any of the following occur: (1) more than 4 subjects drop out because of adverse events probably or definitely **due to study drug** or (2) more than two subjects experience a SAE probably or definitely **due to study drug.** If any subject has a major unexpected negative event (serious injury or death) attributable to the drug, this information will be shared with the other subjects who will have the choice to come off the drug and further enrollment will cease while the event is being fully assessed.

Treatment will continue until any of the following take place:

- 1. Loss of seizure control defined as need to add another seizure medication or other seizure treatment (diet or surgery).
- 2. Intolerable toxicity.
- 3. Pregnancy.
- 4. Withdrawal of consent.
- 5. Six month treatment duration completed as per protocol.
- 6. Laboratory results indicate that the subject's liver function test (ALT or AST) has increased in any of the following ways:
 - >8xULN
 - >5xULN for more than 2 weeks
 - >3xULN and either (TBL >2xULN or INR >1.5)
 - >3xULN with the appearance of fatigue, nausea, vomiting, right upper quadrant pain or tenderness, fever, rash, and/or eosinophilia (>5%)
 - g. Description of what happens to participants receiving therapy when study ends or if a participant's participation in the study ends prematurely.

Extension Phase:

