Data Safety and Monitoring Plan: The Study Chair ([name]) has primary oversight responsibility of this clinical trial. [name] and the sub-investigators will comprise the Safety Monitoring Committee. The Safety Monitoring Committee will review accrual, patterns and frequencies of all adverse events, and protocol compliance every month. They will review data together every month for this small pilot trial by 1) Reviewing and analyzing the progress of the study; 2) Monitoring the safety of the study treatments and diagnostic procedures; 3) Ensuring data quality; 4) Recommending early stopping or continuation of the trial (if applicable); and 5) Reviewing recruitment and event rates. They will assess the proportion of enrolled versus projected enrollment and proportion of subjects who have completed the trial. The Study Chair will provide Safety Monitoring Committee reports and meeting summaries to Greenwich Biosciences regarding the continuation status of the protocol.

The research coordinator at will make safety calls and/or email/text contact with each participant bimonthly to ensure follow-up and assessment of any adverse events. Also, subjects will be asked to keep daily diaries of any side effects or concerns and asked to email or fax them in on a bimonthly basis. If any adverse events have occurred, the PIs will be notified immediately and corrective actions will take place. While patients with Sturge-Weber syndrome can have serious medical issues, we do not expect any serious adverse events (SAEs) directly attributable to the study drug. Occurrence of an SAE directly attributable to the study drug will trigger a review to consider stopping the participant on the study within one month of

the event. Based on a prior study, an adverse event rate of approximately 1 event /subject/month is expected. An adverse event rate more than double this event rate will trigger an in-depth review to consider whether to consider continuing the participant on the study; an important consideration in this decision will be whether the adverse events are considered to be due to the study drug or not.

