- Within 24 hours (of learning of the event), investigators must report any reportable Serious Adverse Event (SAE) that:
 - 1. Is considered life-threatening/disabling or results in death of subject

-OR-

- 2. Is Unexpected/Unanticipated
- Investigators must report all other reportable SAEs within 5 working days (of learning of the event).
- All other (suspected) reportable AEs must be reported within 14 working days of the notification of the event or of the site becoming aware of the event.

Local institutional reporting requirements to IRBs, any GCRC oversight committee and the FDA, if appropriate, remain the responsibility of the treating physician and the Study Chair.

Protocol deviations: that constitute unanticipated problems involving risks require prompt reporting to the JHM IRB. Protocol deviations which impact data results or integrity will also be reported to Greenwich Biosciences.

A protocol deviation that constitutes an "unanticipated problem involving risks to subjects or to others" for the definition of an unanticipated problem) must be reported promptly to the IRB, as follows:

- a. *Emergency deviations:* When a deviation occurs in an *emergency situation*, such as when a departure from the protocol is required to protect the life or physical well-being of a participant. The sponsor and the reviewing IRB must be notified as soon as possible, but not later than 5 days after the *emergency* situation occurred. The PI must submit a report to the JHM IRB.
- b. *Major*, *non-emergent deviations without prior approval*: A planned deviation that is non-emergent and represents a major change in the protocol as approved by the IRB. The IRB must approve the request before the proposed change is implemented. The PI must submit non-emergent deviations to the IRB for review in eIRB under the Further Study Action

activity, and use the Change in Research activity; for paper studies, submit a Change in Research form.

Protocol deviations that are only minor or administrative

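### The SAE definition has no limb for other medically important events, so a liver event that ends treatment without hospitalisation may be reported and counted only as a non-serious event

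*Combined protocol and SAP*

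**What the plan says.** **Definition.** Section 4a (Study Procedures) states: "Serious adverse events include those events that: result in death; are life-threatening; require hospitalization or prolongation of existing hospitalization"; and it closes the list with "or create persistent or significant disability, or birth defects". No later section adds a limb.

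**Liver limits.** Section 4f ends a subject's treatment when "Laboratory results indicate that the subject's liver function test (ALT or AST) has increased in any of the following ways". The limits are above 8xULN; above 5xULN for more than 2 weeks; ">3xULN and either (TBL >2xULN or INR >1.5"; and above 3xULN with symptoms such as fatigue or nausea. Neither Section 4f nor the follow-up text in Section 4g says whether such an event is serious.

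**Reporting.** Under the 24-hour limit in Section 8c, "investigators must report any reportable Serious Adverse Event (SAE) that" is fatal, life-threatening or disabling, or is unexpected. Other SAEs have 5 working days. For the rest, "All other (suspected) reportable AEs must be reported within" 14 working days.

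**Stopping.** Sections 4f and 7d stop the study if "more than two subjects experience a SAE probably or definitely" due to study drug, or if more than 4 subjects drop out for adverse events with the same attribution. Section 4g repeats both counts for the extension phase, but there they lead only to consideration of stopping.

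**Individual review.** Section 8b adds: "Occurrence of an SAE directly attributable to the study drug will trigger a review to consider stopping the participant".

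**The concern.** Raised liver enzymes are a named risk (Section 8a), and the plan says that valproate or clobazam can increase it (Sections 8a and 8b). Subjects are followed remotely as outpatients, with blood drawn at local outside laboratories, so a liver event is likely to surface as a laboratory result rather than as an admission. The plan treats such a result as grave enough to end the subject's treatment, yet nothing in the seriousness definition plainly captures it.

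Two things are at stake. One is how quickly the event must leave the study team. The other is whether it counts toward the lower or the higher of the two study-level thresholds. This matters more because there is no control arm and the safety committee consists of the study chair and the sub-investigators (Section 8b). The adverse events are classified by CTCAE (Section 4a), but no section links a grade to seriousness or to a reporting limit, so grading does not fill the gap.

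**Working it through.** The plan states no figure for this point, so there is none to reproduce. The check is a reading of the text followed by an illustration.

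**Step 1: apply the definition.** Take a subject who passes a Section 4f liver limit, is not admitted, and has treatment ended. Death, hospitalisation and birth defects do not apply. Persistent or significant disability is not met by a laboratory result alone. The life-threatening limb is met only if the investigator judges it so. No listed limb is met on the facts given.

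**Step 2: follow the consequences.**

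| | If not classed as an SAE | If classed as an SAE |
|---|---|---|
| Reporting limit (8c) | 14 working days | 24 hours if unexpected or life-threatening/disabling/fatal; otherwise 5 working days |
| SAE rule (4f, 7d), if drug-related | does not count | counts; met at 2 + 1 = 3 subjects |
| Drop-out rule (4f, 7d), if drug-related | counts; met at 4 + 1 = 5 subjects | counts |

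The difference between the 3rd and the 5th subject follows from the plan's own thresholds. It assumes that ending treatment at a liver limit is a drop-out in the sense of the rule.

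**Step 3: illustrate the size.** Inputs: n = 10 subjects on study drug (Sections 4a, 5, 7c); thresholds r = 3 and r = 5 from step 2; and p, an assumed chance per subject of a drug-attributed liver event that ends treatment without hospitalisation. The documents give no value for p.

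Formula: P(X ≥ r) = 1 − Σ C(10, k) p^k (1 − p)^(10 − k), summed over k = 0 to r − 1.

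Worked case, p = 0.20:
- r = 3: 1 − (0.1074 + 0.2684 + 0.3020) = 0.322
- r = 5: subtract also the terms for k = 3 (0.2013) and k = 4 (0.0881), giving 0.033

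| Assumed p | All such events classed as SAEs (≥3) | Drop-outs only (≥5) |
|---|---|---|
| 5% | 1.2% | 0.01% |
| 10% | 7.0% | 0.2% |
| 20% | 32% | 3.3% |
| 30% | 62% | 15% |

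With n = 11, the number that may be consented, the pairs at 10%, 20% and 30% are 9.0% and 0.3%, 38% and 5.0%, and 69% and 21%. The calculation leaves out replacement of subjects who withdraw in the first two months (Section 4f), any enrolment halt, and events of other kinds. The middle column is an upper bound for the change proposed below, because not every liver-limit event would be judged serious.

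**The case against.** A reader might infer that such an event is automatically non-serious, that the missing limb alone keeps it from 24-hour reporting, and that three or four cases could not stop the study. The documents do not support any of these.

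- **Classification is not automatic.** Section 4a says that SAEs *include* the listed events, and an investigator may judge raised enzymes with raised bilirubin or INR to be life-threatening. This stands. However, no criterion guides the judgement, so two similar cases could be classed differently.
- **Seriousness is not the only gate to 24 hours.** Section 8c also requires the SAE to be fatal, life-threatening, disabling or unexpected. Enzyme rises are listed risks, so a new limb would sometimes give 5 working days. But Section 4a makes severity part of expectedness, and Section 8a describes the known effects as generally mild. A severe case could therefore be unexpected, and then the missing limb is what withholds the 24-hour limit.
- **Other safeguards exist.** Sections 4f and 7d halt enrolment after one major unexpected *serious injury* attributed to the drug, and Section 7d adds a decision on whether to continue. Section 8b requires immediate notice of any adverse event to the investigators and monthly committee review, and the committee can recommend stopping at any count. Section 7c adds a weekly safety review, and Section 8c prompt notice to the principal investigator. These matter. But *serious injury* is not defined, and none of them makes the event count as an SAE.
- **The individual review in Section 8b adds little here**, because the subject's treatment has already ended. This stands, and that review carries no weight in the conclusion.
- **The rates are assumed.** The only Sturge-Weber figure, one transient, indirectly related AST rise in 5 subjects (Section 8a), is not described as ending treatment and does not estimate p. This stands, and it is why the low rates are shown beside the high ones.

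**Conclusion.** The gap is real but limited. Read literally, an unhospitalised liver event that ends treatment meets no listed seriousness limb on that fact alone. It then has a 14-working-day reporting limit and, if judged probably or definitely due to the drug, moves the study toward a stop at the 5th subject rather than the 3rd. That much rests on the text, with two conditions: the investigator does not judge the event life-threatening, and ending treatment counts as dropping out. The probabilities rest on assumed rates and show only how far apart the two thresholds lie. At 5% or 10% the rule is rarely met on either count; the difference becomes large at 20% and above. It does not follow that the study would continue unchecked, since enrolment can be halted and the committee can recommend stopping. This is a cheap improvement to the safety rules, not a fault that undermines the trial.

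**What to change.** Add to the Section 4a definition a limb for important medical events that may jeopardise the subject or need intervention to prevent one of the listed outcomes. State that each event meeting a Section 4f liver limit is assessed for seriousness under that limb. Then reconcile Sections 4a, 4f, 4g, 7d, 8b and 8c so that events judged serious follow the SAE timeline and count toward the existing SAE rule when drug-related.

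Leave the liver limits and the stopping counts as they are. Do not class every liver-limit event as serious in advance: the limits include enzymes above 3xULN with fatigue or nausea, and a blanket rule would settle the question before the assessment is made.

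The cost is a short amendment, a few more expedited reports, and a somewhat higher chance that the existing SAE rule is met.
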